The Attitude-Social Influence-Efficacy (ASE) model (De Vries & Mudde, 1998) frames adherence to medication as deriving from attitudes (A), social influence (S), and self-efficacy (E). However, adherence also requires intact prospective memory, the ability to remember to do a behavior in the future, which tends to be impaired in those with BD (Bogner, de Vries, O'Donnell, & Morales, 2013; Lee et al., 2010; Zogg, Woods, Saucedo, Wiebe, & Simoni, 2012). Given this deficit, even when an individual has the intention to take medication, they lack the planning or organizational abilities to do so consistently (Zogg et al., 2012). Thus, in order to change and sustain medication adherence in this and similar populations, one must address both ASE and prospective memory. This m-Health intervention primes habit formation by targeting behavioral intention using customized psychoeducational and motivational texts with social reference followed by contextual cues, reminders, and immediate positive reinforcement, to create a strong and automatic habit of taking medication which will be sustainable despite variability over time in behavioral intent.

[figure not shown]

Figure 1: Diagram of expanded ASE model

This study aims to test the feasibility, acceptability and effectiveness of a customized m-Health texting intervention built on the Individualized Texting for Adherence Building (iTAB) platform on antihypertensive adherence and systolic blood pressure in hypertensive persons with BD. This practical, customized intervention, intended to improve adherence to antihypertensives and BD medication among high risk individuals, will be suitable for implementation in either primary care or mental health settings and may reverse the unacceptably high morbidity and mortality in this population.

This study has one specific aim:

**Specific Aim 1:** To test the acceptability, feasibility and effectiveness of iTAB-CV to improve adherence to antihypertensives based on self-reported Tablets Routine Questionnaire (TRQ) and a medication event monitoring system (eCAP).

**Hypothesis 1:** iTAB-CV will improve adherence to antihypertensives in non-adherent persons with BD and HTN.

**Hypothesis 2:** Participants will respond to at least 75% of text messages.

**Hypothesis 3:** At least 75% of participants will find iTAB-CV acceptable based on exit interviews.

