**Methods:**

**Overview:**

This study will test an adherence intervention (iTAB-CV) delivered via interactive text messaging which first targets behavioral intent and then adds cues/reminders and reinforcement to form the habit of taking antihypertensives in non-adherent individuals with BD. Thirty eight individuals with BD and HTN being treated with evidence-based antihypertensive agents and mood stabilizing or antipsychotic medications who are non-adherent with their HTN medicine will be enrolled. This phase uses a prospective cohort design with participants serving as their own control. We will test the iTAB-CV intervention quantitatively for feasibility and acceptability as well as for efficacy in increasing adherence to antihypertensives, decreasing systolic blood pressure, and increasing adherence to BD medication.

[figure not shown]

Figure 2: Diagram of Phase II Design

All study participants will be followed for a 3-month period. iTAB-CV, delivered via mobile phone, is intended to be a brief adjunct to standard primary care and mental health treatment. All individuals will continue to receive

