### **Specific Procedures:**

In phase 2, all eligible participants will receive iTAB-CV. After providing informed consent, all participants will undergo screening followed by a 30-day run-in period in which adherence will be measured using eCAP and self-report. During the 30-day run-in period, participants will continue to receive care as usual and serve as their own control with no intervention. Participants will be provided with the eCAP device for the antihypertensive agent that is missed most often. In the case of more than one such agent, the antihypertensive dosed most often. If there is again more than one such agent, the most recently prescribed agent will be chosen. Based on our experience with MEMs, the Hawthorne effect wears off after 1-2 weeks. After the 30-day run-in period, participants will receive 30 days of stage one of iTAB-CV. The study PI or study staff will conduct an interview in order to customize iTAB-CV for each participant at the baseline session.

In stage one of iTAB-CV, participants begin receiving 1 daily educational/motivational customized text messages addressing medication attitudes, social influences, and self-efficacy which will alternate between antihypertensives and BD medications without reminders and 1 daily mood rating. Participants will identify any stems that they don't want to receive and can write in their own personalized messages. At the 8 week meeting, the study PI or study staff will conduct a brief 2nd iTAB-CV interview to determine the types of medications taken (antihypertensives and/or bipolar medications) and at which times of day as well as to pick reminders/reinforcement texts that the participant wants to receive for stage two.

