**b. eCAP:** Study participants will be given an eCAP device for one of their pill bottles, which will record time/date of bottle opening. eCAP will be used for the antihypertensive medication that the patient missed the most frequently in the past week (in the case of multiple antihypertensive medications missed the same proportion of times, the medication dosed most often will be chosen). This method was chosen over monitoring all medications to limit burden, and is appropriate since eCAP is used to confirm the TRQ. A dose will be counted as “taken” if the bottle is opened within six hours of the prescribed time. We will calculate a percent of doses taken by dividing the number of times the bottle is opened by the number of times it should have been opened as per the prescription. Participants who use organizers rather than bottles will be instructed to open and then shut an empty bottle with an eCAP as a “diary” each time they open their pill organizers. Participants will be given the eCAP at the screening visit if they fit inclusion/exclusion criteria. eCAP will be assessed at the baseline visit based upon pill-taking behavior during the interval between screening and baseline visit. Baseline visits will be targeted at 4 weeks after completion of the screening visit. At screening, participants will be asked when their index drug is up for a refill. They will then be reminded to refill their index drug and fill their eCAP via the iTAB-CV system.

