If serious and unexpected adverse events occur, or any other unanticipated problems involving risks to subjects or others, the IRB will be notified. This notification will indicate what serious adverse events were noted, whether they appeared related to the trial, and whether the trial was approved to continue. If found to be related to the trial, the PI will institute appropriate procedures, notify the NHLBI Project Officer, and report such events to appropriate institutional officials and the Office for Human Research Protections.

**Data Analysis plan:** The aim of this project is to test the use of iTAB-CV in a pilot feasibility, acceptability and preliminary efficacy study in a sample of 38 individuals with BD and HTN. Hypothesis: iTAB-CV will be feasible to conduct in an outpatient setting, will be acceptable to participants, and will be associated with improved HTN medication adherence among at-risk individuals with BD and HTN. Treatment acceptability/satisfaction will be measured via a self-report questionnaire and feasibility will be evaluated by percentage of texts answered. The primary dependent measure will be treatment adherence of antihypertensives evaluated with Tablets Routine Questionnaire (TRQ). Adherence will also be measured objectively through eCAP. The measurements will be taken at screening, baseline (4 weeks), 8 weeks, and 12 weeks follow-up. Of primary inferential focus is whether there is change in adherence from baseline to 12 weeks. Adherence will be calculated as a proportion of prescribed medications taken in the past week and will be assessed for each regularly scheduled maintenance agent for HTN prescribed for three months or longer on a daily, routine basis. For individuals who are on more than one such agent, adherence will be assessed for each agent and an average will be

calculated. TRQ will be the main adherence measure, but eCAP will also be analyzed and compared with the TRQ. Secondary outcome measures are: Systolic blood pressure, TRQ for antipsychotic and/or mood stabilizers, psychiatric symptoms (BPRS health utilization, Medication Adherence Self-Efficacy Scale - Revised, Self-Report Habit Index (64), Brief Illness Perception Questionnaire, Beliefs About Medicines Questionnaire, AMSQ, treatment acceptability/satisfaction by questionnaire and exit interviews, and feasibility via % texts answered.

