Main Hypothesis Testing: A paired t-test will be used to test significance for the TRQ and eCAP adherence outcomes from baseline to 12-week follow-up. Nonparametric tests will also be considered. Secondary Hypothesis Testing: Difference from baseline to 8 weeks, and 8 weeks to 12 weeks will also be analyzed. Corresponding TRQ and eCAP values will be correlated and Bland-Altman plots will be used to help identify discrepancies. Correlations will be computed for change in antihypertensive adherence values versus changes in TRQ for antipsychotic and/or mood stabilizers, medication attitudes, self-efficacy, and habit strength. Exploratory longitudinal mixed models will be used to analyze repeated measurements at baseline, 8 weeks, and 12 weeks. Note that the preliminary analyses and model estimates will inform the future design of a more extensive study involving a controlled trial.

Attrition Analyses: Preliminary analyses will determine factors that are associated with attrition effects. Attrition rates in a current BD adherence study at our institution is < 30%. Differential attrition by key covariates such as age and gender will be examined, such as through log rank tests. Power Analysis: Given the preliminary data from a prior BD adherence study (35), difference in oral medication adherence after treatment was 21.7%. Standard deviation of this difference was 39%, resulting in an effect size of 0.56. We expect to observe a similar if not greater effect size. Using a t-test of difference between baseline and 12 week TRQ, power is 0.80 at two-sided alpha = 0.05 for a sample of 38 subjects to reject a null hypothesis of no change in adherence when effect size is 0.549, and attrition is 25%. The projected sample size should thus provide adequate power to detect expected changes in anti-hypertensive drug adherence levels.

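### The self-reported (TRQ) and electronic (eCAP) adherence changes are tested separately, but the difference between them is not estimated, so a shift in over-reporting under the intervention would not be measured

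*Combined protocol and SAP*

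**What the plan says.** **Ranking of the measures.** The Data Analysis plan states: "The primary dependent measure will be treatment adherence of antihypertensives evaluated with Tablets Routine Questionnaire (TRQ"). It adds: "TRQ will be the main adherence measure, but eCAP will also be analyzed and compared with the TRQ". The power statement concerns TRQ only.

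**Role of eCAP.** The eCAP paragraph under Adherence justifies monitoring a single bottle because this "is appropriate since eCAP is used to confirm the TRQ". Specific Aim 1 is nevertheless "based on self-reported Tablets Routine Questionnaire (TRQ) and a medication event monitoring system (eCAP"), and Table 1 lists both measures under primary outcomes.

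**Tests.** Main Hypothesis Testing covers both measures: "A paired t-test will be used to test significance for the TRQ and eCAP adherence outcomes from baseline to 12-week follow-up".

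**Comparison of the measures.** Secondary Hypothesis Testing says: "Corresponding TRQ and eCAP values will be correlated and Bland-Altman plots will be used to help identify discrepancies". The exploratory mixed models name the visits but no term for measure by time. Nothing says what is concluded if TRQ improves and eCAP does not.

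**Design.** The Overview states: "This phase uses a prospective cohort design with participants serving as their own control". After the week 4 baseline, "participants begin receiving 1 daily educational/motivational customized text messages addressing medication attitudes, social influences, and self-efficacy"; reminders and reinforcement are added from week 8. A study research assistant administers the measures, and no blinding is described.

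**The concern.** The result of interest is a change in TRQ. Over-reporting by the same amount at both visits cancels. Over-reporting that grows between week 4, before any text, and week 12, after eight weeks of messages from the study about taking medication, does not cancel and looks like a gain in adherence. With no concurrent group, nothing else in the design absorbs such a shift.

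eCAP is the instrument that could expose it. The quantity needed is the TRQ change minus the eCAP change in the same people, and the plan does not estimate it. Two separate p-values are no substitute: one significant and one non-significant result do not test whether the two changes differ.

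The plan says that its estimates will inform a later controlled trial. A TRQ gain inflated by reporting would carry into that trial's assumed effect.

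**Working it through.** **Inputs from the Data Analysis plan.** N = 38; attrition 25%; mean change 21.7 points; SD of change 39 points; two-sided alpha 0.05; power 0.80 at effect size 0.549.

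**1. The plan's own figure.** 21.7/39 = 0.556, stated as 0.56. Completers: 38 × 0.75 = 28.5, taken as 28. Paired t-test power from the noncentral t distribution at effect size 0.549 is 0.800 with 28 pairs and 0.814 with 29. The stated power reproduces and is not in dispute.

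**2. Which reporting error matters.** Write TRQ = A + b and eCAP = A + e, where A is true adherence and b and e are the measurement errors.
- TRQ change = ΔA + Δb. A constant b drops out.
- Change in gap = TRQ change − eCAP change = Δb − Δe. This estimates the reporting shift only if eCAP error is stable (Δe = 0).

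**3. What the planned comparison shows.** Adding the same number of points to every week 12 TRQ value leaves the week 12 correlation with eCAP unchanged, so correlation is blind to a mean shift. A Bland-Altman plot gives a mean difference in level. If visits are pooled in equal numbers and the gap is g at week 4 and g + 10 at week 12, the pooled bias is g + 5 and the shift is hidden. Plots made and compared by visit would show it, but the plan does not specify that.

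**4. Illustration for the TRQ test alone.** Set ΔA = 0, n = 28, SD 39. The standard error is 39/√28 = 7.37. The smallest significant mean change is t(0.975, 27) × 7.37 = 15.1 points. The noncentrality is shift/7.37.

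| Assumed reporting shift (points) | Probability that the TRQ test is significant |
|---|---|
| 5 | 0.10 |
| 10 | 0.26 |
| 15 | 0.50 |

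The shift sizes are assumptions; the documents give none.

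**5. Precision of the proposed estimate.** The SD of the gap change is not in the documents. Assume SD 39 for each change and correlation ρ between them. Then SD = 39 × √(2(1 − ρ)), and the 95% half-width = t(0.975, 27) × SD/√28.

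| ρ | SD of gap change | 95% half-width | Widening detectable at 80% power |
|---|---|---|---|
| 0 | 55.2 | 21.4 | 30.3 |
| 0.5 | 39.0 | 15.1 | 21.4 |
| 0.7 | 30.2 | 11.7 | 16.6 |
| 0.8 | 24.7 | 9.6 | 13.5 |

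At ρ = 0.5, a true widening of 10 points would be detected with power of only 0.26. A non-significant result would not rule out a material shift, so this should be an estimate with an interval and not a pass/fail test.

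**The case against.** A reader might infer that Hypothesis 1 rests on self-report alone and that the plan looks only for discrepancies. The documents do not support that. The eCAP change is tested over the same interval under Main Hypothesis Testing, the aim names both measures, and Table 1 lists both as primary outcomes. A gain due purely to reporting should appear as a TRQ gain without an eCAP gain.

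A reader might also take 10%, 26% and 50% as the chance of a false claim about adherence. That would need a rule that TRQ significance suffices whatever eCAP shows, and no such rule is stated. If the mean of eCAP truly does not change, both tests are significant in the favourable direction at most about 2.5% of the time, because the eCAP test alone reaches its upper tail that often.

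It is also fair to say that the mean gap change is simply one mean change minus the other, that systolic blood pressure offers a further check that is not self-reported, and that this is a pilot.

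The objection removes the stronger readings but leaves the gap. The two planned means are not like for like: TRQ averages all antihypertensives over the past week, while eCAP covers one drug and, at baseline, the whole run-in. Subtracting them gives neither a matched difference nor an interval. TRQ is still ranked as the main measure, with no statement on discordant results.

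eCAP also has limits as a yardstick. Pill-organizer users open an empty bottle as a diary. A dose counts only if the bottle is opened within six hours of the prescribed time, so timed reminders could raise eCAP through better timing alone and narrow the gap.

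**Conclusion.** The point holds in a limited form. Both changes are tested, but their difference is not estimated, and the planned correlation and Bland-Altman plots do not show whether over-reporting shifts between week 4 and week 12. The plan therefore lacks the estimate that would let eCAP confirm a change in TRQ, as opposed to a level.

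The size of any bias is unknown. The illustrative probabilities apply to the TRQ test alone and rest on 28 pairs, no true change, assumed shifts, and an SD of 39 taken from a prior bipolar adherence study. The precision range further assumes that SD for the eCAP change and a correlation of 0 to 0.8. The stated power is unaffected. This is an inexpensive improvement to the plan and does not invalidate the primary test.

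**What to change.** Add to Secondary Hypothesis Testing:
- For the eCAP index drug, compute gap = TRQ percent taken minus eCAP percent at week 4 and at week 12. Use that drug's own TRQ, and cut eCAP to the same past-week days. TRQ is assessed per drug and eCAP records date and time, so both are available.
- Report the mean paired change in gap with a 95% CI, as an estimate and not a pass/fail test.
- Make the Bland-Altman plots separately by visit.
- Repeat the estimate without pill-organizer users, whose eCAP record is a diary.
- Note that eCAP can rise through better dose timing under the six-hour rule, which would mask a reporting shift.

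Add one sentence on interpretation: a TRQ gain is reported as improved self-reported adherence, and is presented with the eCAP change and the CI for the gap change before any conclusion that adherence improved.

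The cost is a few extra summaries from data already scheduled, a slightly more guarded claim, and an interval that will be wide at this sample size.

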**Table 1: Schedule of Assessments and Study Events**

Procedure	Screen	Baseline	Visit 1	Visit 2
Visit Timing	Day 0	Week 4	Week 8	Week 12
Informed Consent	X			
Inclusion/Exclusion	X			
Demographics, Charlson, medical history	X			
Diagnosis: Mini-International Neuropsychiatric Interview	X			
Prospective Memory: The Memory for Intentions Screening Test (MIST)	X			
Rapid Estimate of Adult Literacy in Medicine – Short Form (REALM-SF)	X			
Brief Illness Perception Questionnaire (Brief IPQ)	X		X	X
Medication Adherence Self-Efficacy Scale - Revised (MASES-R)	X		X	X
Medication Attitudes – Beliefs About Medicines Questionnaire, AMSQ	X		X	X
Self-Report Habit Index	X	X	X	X
Primary outcomes:				
Average TRQ for antihypertensive agents	X	X	X	X
eCAP for antihypertensive agent		X	X	X
Secondary outcomes:				
Systolic Blood Pressure	X	X	X	X
Height (Screen only) and weight / BMI	X	X	X	X
Average TRQ for bipolar medications	X	X	X	X
Brief Psychiatric Rating Scale (BPRS)	X	X	X	X
Montgomery-Åsberg Depression Rating Scale (MADRS)	X	X	X	X
Young Mania Rating Scale (YMRS)	X	X	X	X
Introduction of eCAP for antihypertensive	X			
Brief powerpoint presentation providing psychoeducation on hypertension and bipolar disorder		X		
iTAB-CV interview and training; iTAB-CV stage 1 - initiation of behavioral priming via text + daily mood monitoring; phone given at this time		X		
iTAB-CV stage 2 – brief interview regarding iTAB-CV; frequency of text; choose stems for reminders and reinforcement			X	
Participant acceptability/satisfaction/feasibility/exit interviews				X

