**Exploratory Aims:** *Secondary outcomes* Change in systolic BP, change in TRQ for BD medications, change in attitudes and self-efficacy for adherence, health status, healthcare utilization (number of hospitalizations and ER admissions), and psychiatric symptoms. Habit strength, prospective memory and mood will be evaluated as possible variables of interest.

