treatment as usual with their regular provider(s). Individuals who meet eligibility criteria will have a 30 day run-in period in which their medication adherence will be measured with TRQ and MEMS but without an additional intervention. Following the run-in period, Stage 1 of the iTAB-CV intervention will be introduced. A member of the study team will conduct an interview in order to customize iTAB-CV for each participant at the baseline session. In the first month of iTAB-CV, participants will receive alternating daily texts with psychoeducational and motivational content once daily and a daily mood rating request to both monitor their mood and to determine engagement with the iTAB-CV intervention. In the second stage of iTAB-CV, participants will receive daily texts which will include medication reminders, contextual cues, and immediate reinforcement for medication taking behavior in addition to the content from stage 1. Assessments that include evaluation of treatment adherence, psychiatric symptoms, self-efficacy for medication taking behavior, illness beliefs, medication attitudes, and habit strength for both antihypertensive and BD medications will be conducted at four time points over a 3-month time period (screening, baseline/week 4, week 8, and week 12). Blood pressure will be measured at each of the four contacts. Individuals who drop out of the intervention, and who agree, will be followed up with outcomes assessments over the same 3-month time period that they would have been evaluated had they remained in the study.

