Stage two of iTAB-CV includes the addition of customized context cues/reminders and immediate reinforcement for medication taking behavior in addition to 1 daily motivational mood rating. The number of texts per day will be determined based on the number of times a day that medications are prescribed (up to four a day). Assessments that include evaluation of treatment adherence, psychiatric symptoms, health status, self-efficacy for medication taking behavior, illness beliefs, medication attitudes, and habit strength for both antihypertensive and BD medications will be conducted at four time points over a 3-month time period (screening, baseline/week 4, week 8, and week 12). Blood pressure and weight will be measured at each of the four contacts. Height will be measured at screen. Individuals who drop out of the intervention, and who agree, will be followed up with outcomes assessments over the same 3-month time period that they would have been evaluated had they remained in the study. Table 1 outlines the study schedule of events/assessments.

Individuals will receive reminder telephone calls or text messages during the 2 weeks prior to their scheduled appointment. Individuals will be requested to provide three additional contacts who may assist in facilitating contact with the participant should the individual miss follow-up appointments and if difficulty arises in contacting the individual to re-schedule follow-up (for example, change of address or telephone number). In order to optimize study retention, study staff will maintain personal contacts with study participants via greeting/post cards for birthdays and holidays and regular contact for "location checks" between assessment periods.

One month post study completion, the PI or research study staff will call the individual and will administer the TRQ over the phone for bipolar and blood pressure medications.

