We will also send text messages once a week that reinforce good adherence to responding to text messages to keep participants engaged (e.g., "Great job responding to all the messages this week!") (See Appendix #3

for sample texts). If they did not respond, they will be encouraged to do so moving forward (e.g. “We really want to hear from you; we hope you will respond to your messages next week!”).

**Electronic Reminder Device:** We will provide participants with mobile devices and we will purchase bulk ‘minutes’ in order to provide the text message intervention. Importantly, participants will not be responsible should they lose or break the device. Participants may use the device for other purposes (e.g., phone calls, calendar functions) as they wish. Participants along with research staff will collaboratively identify a time during the day in which the reminders will occur. Once enrolled in the study, participants will receive full compensation even if they miss all reminders.

**Psychoeducation and training to use electronic device:** All participants will receive a standardized brief psychoeducational presentation with information about hypertension and bipolar disorder as well as training on how to use the electronic device at the 4 week visit.

Participants will respond to a daily mood rating text once a day at the end of the day. Indication of severe low or high moods will trigger an automated text that will direct the participant to go to the ER in case of emergency. After 3 such texts, the system will automatically notify study staff who will follow up with the participant with a phone call.

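### Table 1 omits the week-4 visit for the Brief IPQ, MASES-R, BMQ and AMSQ, although the text schedules it and week 4 is the plan's own baseline

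*Combined protocol and SAP*

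**What the plan says.** The Overview lists the constructs to be assessed, among them "self-efficacy for medication taking behavior, illness beliefs, medication attitudes, and habit strength for both antihypertensive and BD medications". Specific Procedures repeats the list, adding health status, and says that these assessments "will be conducted at four time points over a 3-month time period (screening, baseline/week 4, week 8, and week 12"). Neither section exempts any instrument.

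Table 1 gives a different schedule. The Brief IPQ row, the row "Medication Adherence Self-Efficacy Scale - Revised (MASES-R" and the combined BMQ/AMSQ row are marked at Screen, Week 8 and Week 12, and their Baseline (Week 4) cell is empty. The Self-Report Habit Index (SRHI), which belongs to the same list of constructs, is marked at all four visits.

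The Data Analysis plan fixes which visit is baseline: "The measurements will be taken at screening, baseline (4 weeks), 8 weeks, and 12 weeks follow-up". The Compensation section and the Table 1 column heading agree. The same plan names all four instruments as secondary outcome measures: the MASES-R, then the SRHI, then "Brief Illness Perception Questionnaire, Beliefs About Medicines Questionnaire, AMSQ". The Exploratory Aims state the outcome as "change in attitudes and self-efficacy for adherence".

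**The concern.** Staff cannot follow both schedules. If they follow Table 1, the only value of these four scales before the intervention is the one at Day 0, about four weeks before iTAB-CV starts.

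This matters because the study has a single arm. Participants are their own controls, so pre-post change is the only evidence on these constructs. Stage one, from week 4 to week 8, consists of "educational/motivational customized text messages addressing medication attitudes, social influences, and self-efficacy", so it acts directly on what the MASES-R, BMQ and AMSQ measure. Without a week-4 value, stage-one change in these scales cannot be separated from whatever happened during the run-in, and a value not collected at that visit cannot be recovered later. The plan also says that its estimates will inform a later controlled trial.

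**Working it through.** **The plan's one computed design figure.** The stated power of 0.80 (38 enrolled, 25% attrition, effect size 0.549, two-sided alpha 0.05, paired t-test) reproduces: 38 × 0.75 = 28.5, and 28 completers give 0.7997. It concerns the TRQ, so this point does not touch it. The rest is a comparison of schedules.

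**Is the blank real?** Table 1 has 12 rows for repeated measures.

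| Rows | Screen | Week 4 | Week 8 | Week 12 |
|---|---|---|---|---|
| SRHI, both TRQ rows, systolic BP, weight/BMI, BPRS, MADRS, YMRS (8 rows) | X | X | X | X |
| eCAP (1 row; device issued at screening) | – | X | X | X |
| Brief IPQ; MASES-R; BMQ/AMSQ (3 rows, 4 scales) | X | – | X | X |

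The three affected rows keep an empty second cell where neighbouring rows have a mark. This does not look like a fault in how the table was read.

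**Data lost if Table 1 is followed.**
- Scale-visits in the text: 4 scales × 4 visits = 16.
- Scale-visits in Table 1: 4 × 3 = 12.
- Missing: 16 − 12 = 4 (25%), all at week 4. With 38 participants this is at most 38 × 4 = 152 completed scales.

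**Changes that can be computed.** Take the windows that the Data Analysis plan uses: weeks 4–8, 4–12 and 8–12.
- Scale-by-window changes: 4 × 3 = 12.
- Needing week 4: 4 × 2 = 8, not computable.
- Remaining: 4 (weeks 8–12).
- A mixed model at baseline, 8 and 12 weeks would have 2 of its 3 time points for any of these scales.

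The plan does not say which outcomes its differences and mixed models cover. These counts therefore describe what the data would allow, not analyses expressly promised for each scale.

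**What change from screening measures.** Let M0, M4, M8 and M12 be a scale's values at screening and weeks 4, 8 and 12, and let d = M4 − M0 be the run-in change. Then

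- M8 − M0 = (M8 − M4) + d
- M12 − M0 = (M12 − M4) + d

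Change from screening therefore differs from change since baseline by exactly d. The documents give no value for d.

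**Correlations.** The plan correlates change in antihypertensive adherence with change in attitudes and in self-efficacy (the Brief IPQ is not named). If adherence change runs from week 4 to week 12 (12 − 4 = 8 weeks), scale change could only run from week 0 to week 12 (12 weeks), of which 4 precede the intervention. Whether this weakens the correlations depends on covariances that the documents do not give. The effect may be nil.

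**The case against.** The best defence is that the table is right and the sentence in the text is a loose summary. The Specific Procedures version also puts health status at four visits, although Table 1 has no repeated row of that name. It puts treatment adherence at four visits, although eCAP cannot have a screening value. It then refers the reader to Table 1. The blank falls in three adjacent rows, at a visit already loaded with the presentation, interview and training. A deliberate omission is plausible, and this part of the objection stands. However, the documents do not say so, and no passage names screening as the reference visit for these scales.

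A second argument is that a pre-intervention value exists at screening, so pre-post change can still be estimated and a model on screening, week 8 and week 12 has three points. That is true, but the estimate then includes the run-in, and the plan's mixed models are specified at baseline, 8 and 12 weeks.

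Third, the TRQ is also collected at screening, so TRQ correlations could be matched on screening to week 12. They could, but participants are selected on poor TRQ adherence at screening, so that change starts from a selected value and again includes the run-in. eCAP cannot be matched this way at all.

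Finally, these outcomes are secondary and sit under exploratory aims. That limits the severity but does not resolve the contradiction.

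**Conclusion.** The concern holds. Text and table contradict each other on week 4 for four secondary outcome scales. If Table 1 is followed, none of the four has a value at the visit that the plan defines as baseline: 4 of 16 scale-visits are lost, and 8 of 12 scale-by-window changes cannot be computed. The second count assumes that the plan's three change windows are applied to all four scales.

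The only remaining pre-post estimate is shifted by the run-in change d, whose size and sign are unknown. Changes from week 8 to week 12, the primary TRQ and eCAP tests and the stated power are unaffected. This should be fixed, but it does not threaten the main result.

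**What to change.** Reconcile Table 1 with the Overview and Specific Procedures, in one of two ways.

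1. **Collect the scales at week 4, as the text says.** Mark Baseline (Week 4) in the three Table 1 rows. Have the scales completed before that visit's iTAB-CV interview and before the session that combines psychoeducation with "training on how to use the electronic device at the 4 week visit", so that the value precedes all intervention. State in the Data Analysis plan that week 4 is the start of change for both these scales and adherence in the differences, correlations and mixed models. Reporting change from screening to week 4 is optional.
2. **If the blank is deliberate,** correct the two text sections, name screening as the reference visit for these scales, and label their change from screening as including the run-in.

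The first option costs at least 9 + 13 + 18 + 19 = 59 questionnaire items per participant (Brief IPQ, MASES-R, BMQ, AMSQ) at a visit already held. It costs more if scales are completed separately for antihypertensive and BD medicines. It also needs three table marks and a short statement of the change window. The second option costs only text. Neither changes the sample size.
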